5.3 SCREEN FAILURES

Patients who are consented, but do not meet inclusion and exclusion criteria, will be withdrawn from the trial by the PI.

6 STUDY INTERVENTION(S) OR EXPERIMENTAL MANIPULATION(S)

6.1 STUDY INTERVENTION(S) OR EXPERIMENTAL MANIPULATION(S) ADMINISTRATION

6.1.1 STUDY INTERVENTION OR EXPERIMENTAL MANIPULATION DESCRIPTION

As described in Section 2.2 Background, CoCM is a stepped care model, and the intensity of treatment is determined by the needs of the patient and is therefore variable (i.e., there is no fixed number or duration for interventions contacts). Study participants in both arms of the study will be offered enrollment in the CoCM, but engagement is not required for the participant to contribute data to the evaluation.

Table 1 – Description of CoCM Fundamental Principles and MOUD Core Components		
CoCM Principles	Intervention	
	Control Group	Additions for Intervention Group
Team Based: A team of providers working together using a shared care plan	
 Prepared, proactive primary care practice Minimum three-person CoCM team 
 PCP diagnoses MH disorders PCP prescribes psychotropic medications CM provides care coordination Psychiatrist provides TX recommendations Case reviews with CM and psychiatrist to discuss MHS Clear communication strategies Shared medical record 	
 Integration 
 Intervention team 
 PCP diagnoses OUD Case reviews with CM and psychiatrist to discuss OUD OUD TX included in shared medical record Pharmacological TX 
 PCP is waivered to prescribe MOUD PCP prescribes MOUD Psychiatrist is waived to prescribe MOUD
Patient-Centered: Shared decision making.	
 Patient education 
 Patients presented with both pharmacotherapy and psychotherapy TX options for MHS Treatment preferences assessed Shared decision making TX and self-management goals set Patient activation 	
 Pharmacological TX 
 Patients presented with pharmacotherapy TX options for OUD with emphasis that medication is essential for good outcomes 
 Transmucosal buprenorphine/Naloxone Extended-release injectable buprenorphine Extended-release injectable naltrexone Psychosocial 
 Patients presented with psychotherapy TX options for OUD
Population-Based: Tracking all patients proactively with a registry	
 Track patients in registry Use registry to proactively identify patients not engaged in care Conduct outreach to patients falling through the cracks 	
 Pharmacological TX 
 CM tracks urine drug screen labs CM checks the state prescription drug monitoring program for prescription fills CM uses call back protocol to assess for medication diversion
Measurement-Based: Systematic use of clinical outcome measures to support treatment to target	
 Screen for MHS using PHQ-9 and GAD-7, and PC-PTSD-5 Monitor symptoms over time with PHQ-9, GAD-7 and PCL-5 Identify patients not responding to TX Intensify TX 
 Switch/Augment psychotropic Augment with psychotherapy Refer for specialty mental health consultation Refer for specialty mental health TX Stepped care 	
 Integration 
 Screen for OUD using NIDA-ASSIST Screen for SUDs using AUDIT-C and BAM Pharmacological TX 
 Monitor OUD patients 
 Opioid withdrawal symptoms Illicit opioid craving Illicit opioid use Medication side effects Urine drug screens Identify patients not responding to treatment Intensify TX 
 Switch/Augment OUD medications Augment with psychotherapy Refer for specialty addiction consultation Refer for specialty addiction TX Stepped care
Evidence-Based: Delivery of evidence-based psychosocial and pharmacological treatments	
 Deliver high fidelity evidence-based psychotherapy for MHS 
 Behavioral Activation Prescribe evidence-based psychotropic medications for MHS 
 Side effect management Address adherence barriers 	
 Psychosocial 
 Deliver high fidelity evidence-based psychotherapy for OUDs 
 Behavioral Activation for SUD Encourage attendance at mutual help groups Pharmacological TX 
 Prescribe MOUD for OUD

	
 Conduct suicide risk assessment and safety planning OUD Treatment Options 
 Refer to specialty addiction treatment for OUD SAMHSA Providers Clinical Support System (MPI [name] – Mentor) 	
Accountable: The team and the health care organization monitor process and outcome measures and conduct QI activities	
 Specify process of care and outcome metrics for MHS Set metric benchmarks for MHS Monitor MHS metrics for providers and clinics Conduct QI for any lower than expected performance on MHS metrics 	
 Integration 
 Specify process of care and outcome metrics for OUD Set metric benchmarks for OUD Monitor OUD metrics for providers and clinics Conduct QI for any lower than expected performance on OUD metrics Monitoring to meet regulatory requirements for buprenorphine/naloxone prescribing

Abbreviations: PCP – Primary Care Providers, CM – Care Manager, TX – Treatment, QI – Quality improvement, SAMHSA - Substance Abuse and Mental Health Services Administration, MHS – Mental Health Symptoms, OUD – Opioid Use Disorder, SUD – Substance Use Disorder.

Intervention

Based on a recent evidence synthesis,⁵⁰ MOUD has three core components: 1) integration of OUD treatment with other MHS and physical health disorders, 2) pharmacological treatment, and 3) psychosocial support.⁵⁰ Table 1 describes the core components of the intervention and the active control. Primary care providers will provide all psychotropic and MOUD medications with consultation from a psychiatrist and support from a care manager. Care managers monitor symptom response using structured instruments and provide behavioral activation. In contrast to the control group, care managers in the intervention group specifically monitor OUD outcomes and the behavioral activation will focus on opioid addiction. Primary care providers in the intervention group will be waivered and expected to prescribe MOUD. Primary care providers in the control group will also be allowed to be waivered and prescribe MOUD.

Mechanism of Action – The hypothesized mechanism of action is MOUD persistence defined as the ratio of the number of days they reported taking the MOUD medication (numerator) to the number of days during the 6-month follow-up period for which it was prescribed (denominator).⁵¹

Integrated Treatment – The treatment of OUD will be integrated with the treatment of MHS, other substance use disorders (SUDs), and physical health disorders. **Team-Based:** The integrated care team will include a care manager, primary care providers and consulting psychiatrist. Consulting psychiatrists will have a buprenorphine waiver and be trained by MPI [name]. **Patient-Centered:** The care manager will educate, activate, promote self-management, assess treatment preferences, and engage in shared decision making. **Population-Based:** The care manager will enter patients in the CMTS registry and conduct outreach activities with those who miss appointments. **Measurement-Based:** OUD, other SUD, and MHS will be assessed over time and stored in CMTS. Care managers will use the PHQ-9 for depression, the GAD-7 for anxiety and the PCL-5 for posttraumatic stress disorder (PTSD). For patients not experiencing a 50% decrease in symptom severity, options for “treating to target” include: 1) increasing dose, 2) switching medications, 3) augmenting medications, and/or 4) intensifying psychosocial interventions. Treatment adherence and side effects will also be monitored and managed. Monitoring OUD symptoms and adherence is described below. **Evidence-based:** The primary care provider will prescribe FDA approved psychotropic medications for depression, anxiety and PTSD concurrently with pharmacologic treatment of OUD (as described below). Care managers will also be

trained to deliver Behavioral Activation (described below). For alcohol, the primary care provider will prescribe one of two FDA approved medications (disulfiram or acamprosate) that can be used with buprenorphine. The care manager will use the AUDIT-C⁵² for measurement based care. For benzodiazepines, the care manager will screen for anxiety and sleep disorders, and if present the consulting psychiatrist will recommend a trial of an SSRI or trazodone. For other SUDs, we will deliver Behavioral Activation and encourage abstinence. Primary care providers will offer appropriate management of physical health disorders common among patients with OUD and MHS such as chronic obstructive pulmonary disease, viral hepatitis, human immunodeficiency virus, and chronic pain.

Pharmacological Treatment/MOUD - Pharmacologic treatment of OUD will rely mainly on transmucosal buprenorphine/naloxone prescribed by primary care providers with DATA 2000 waivers. Frequency of medication self-administration will be tailored for each patient (from 7 day to 30 day supply) based on regularity of appointment attendance, evidence of illicit substance use, and evidence of treatment adherence. Extended-release injectable buprenorphine will also be available for patients with inadequate medication adherence. Some selected patients who agree to complete opioid withdrawal and prefer antagonist treatment can receive extended-release injectable naltrexone. Methadone will not be used because it cannot be prescribed in the primary care setting. Referral to federally licensed opioid treatment programs that dispense methadone will be an option if needed. **Measurement-Based:** Though no studies to our knowledge have used measurement-based care to support OUD treatment, measurement-based care and “*treat to target*” are fundamental principles of CoCM and will be incorporated into the intervention. Care managers will ask four yes/no questions about: 1) opioid withdrawal symptoms, 2) illicit opioid craving, 3) illicit opioid use, 4) medication side effects. Whenever possible, we will corroborate negative self-reports of illicit opioid use with urine drug screens. In addition, care managers will ask patients about medication adherence to make sure patients are taking the medication as prescribed and not waiting for withdrawal symptoms, swallowing the transmucosal medication, or smoking/eating before taking the medication. Self-reported adherence will be corroborated by regular checking of the state prescription drug monitoring program to assure that patients are picking the medication up from the pharmacy. To monitor for medication diversion, we will use a call-back protocol developed by MPI [name] and colleagues.⁵³ All patients will be told about the call-back protocol (as a prevention intervention), but the protocol will only be used when clinically indicated. If called back, patients will be asked to return to the clinic within 24 hours with their MOUD medication supply. If the pill count is short, medication diversion will be presumed, and the patient will be switched to injectable buprenorphine if possible or limited to a 7 day supply. **Treatment to Target:** If the patient is experiencing opioid withdrawal symptoms, illicit opioid craving, or illicit opioid use, the care manager will alert the consulting psychiatrist during the case review. The consulting psychiatrist will then *recommend* a change to the treatment plan to the primary care provider. In the case of buprenorphine/naloxone, options for changing the treatment plan include: 1) increasing the dosage (max dose 32mg), 2) augmenting with clonidine,⁵⁴ 3) switching to injectable buprenorphine, and/or 4) intensifying psychosocial interventions. If the patient is experiencing medication side effects, but not opioid withdrawal symptoms or illicit opioid craving, consideration will be given to lowering the medication dosage. In the case of extended-release naltrexone, only a single dosage is available, so options include: 1) switching to buprenorphine/ naloxone, 2) augmenting with clonidine, and/or 3) intensifying psychosocial interventions.

Psychosocial Support - Psychosocial support will be provided by the care manager under the guidance of the consulting psychiatrist. Care managers will be trained by Co-I [name] to deliver behavioral activation (BA), an established psychosocial intervention for depression and anxiety, and an emerging intervention for PTSD,⁵⁵⁻⁵⁷ OUD,^{58,59} and other SUDs.⁶⁰ BA is a brief and relatively simple therapy that can be delivered by mid-level providers. BA benefits patients with OUD and comorbid MHS because it

helps to counter behavioral avoidance by assisting patients in identifying valued activities and developing strategies for pursuing them in healthy, non-drug use ways. Additionally, because individuals with OUD and comorbid MHS often neglect important aspects of their lives (e.g., wellness and financial obligations), BA is well-suited to helping them systematically address these problems that if left unaddressed are risk factors for relapse. Importantly, use of non-opioid psychoactive substances, including alcohol, will be monitored and addressed in the context of BA treatment as needed.⁶⁰ We will also use BA to assist patients in identifying and engaging family and friends who are supportive of their recovery efforts.⁶¹ This component will also include gentle encouragement to attend mutual help groups such as Narcotics Anonymous. Receipt of specific BA elements will be tracked at the encounter level in the CMTS registry.

Control

The active control will provide integrated treatment for MHS described above, but not treat OUD. Treatment for OUD will involve referral to specialty settings.

6.1.2 ADMINISTRATION AND/OR DOSING

Providers – Providers include the patients regular primary care provider, their assigned care manager and the psychiatric consultant. All providers are routine care staff at the participating clinics.

Care Management Tracking System (CMTS) – For the evaluation, CMTS will be used to measure the number of care manager encounters, the number of care manager encounters with recorded elements of BA, number of psychiatric case reviews, urine test results, medications prescribed for OUD and MHS, as well as results of state prescription drug monitoring checks to obtain an objective measure of MOUD initiation and adherence. For injectable buprenorphine or naltrexone, clinic staff will likewise record the administration of these injections in the CMTS.

6.2 FIDELITY

6.2.1 INTERVENTIONIST TRAINING AND TRACKING

Intervention *fidelity* will play a critical role in this study. If fidelity is artificially controlled, the trial would lack external validity.⁶² If fidelity is poor, we would run the risk of incorrectly concluding that the potential clinical effectiveness of the intervention is not better than the control. Therefore, we will take a *balanced* approach whereby the implementation team will monitor fidelity and use real-world implementation strategies to ensure that each clinic achieves and maintains a sufficient level of fidelity required for the intervention to *potentially* be clinically effective. *External facilitation*^{63,64} will be used to deliver a combination of implementation strategies that the AIMS Center has practice-tested and refined over the years. These implementation strategies are known to be effective for CoCM for MHS⁶⁵, and thus will not be evaluated. For the 12 clinics randomized to implement the intervention *only*, we will conduct an ongoing mixed methods *formative evaluation* to assess implementation success, identify emergent barriers and tailor implementation strategies to improve fidelity. Implementation fidelity will be measured using the intervention fidelity rubric and process measures available in the CMTS registry (e.g., % of patients with regular care manager contacts and psychiatric case reviews).

The AIMS Center has an established implementation approach that includes *training* and *external facilitation* to support practice change required to implement CoCM. Each practice will identify a clinic implementation team, comprised of clinic managers, primary care provider champions, and practice/program managers. Additional team members can include clinic leaders, psychiatric consultant, care manager, and finance/compliance officers. In the **Exploration** phase, the clinic implementation team develops a shared vision, business plan and rationale for undertaking the CoCM practice change including consideration of the *Outer Setting*, *Inner Setting*, and *Intervention Fit* with current clinical capacities and workflow. In the **Preparation** phase, the clinic implementation team focuses on developing clear workflows to deliver the six CoCM fundamental principles. The CoCM/CHAMP team members all complete basic training on CoCM/CHAMP role responsibilities and role specific didactics such as BA training for the care manager or MOUD training/waiver for the primary care provider. During the **Implementation** phase, external facilitation supports the CoCM/CHAMP team to meet process and outcome benchmarks. Role specific learning communities are established to promote adaptations of skills to deliver patient care as a team.

6.3 MEASURES TO MINIMIZE BIAS: RANDOMIZATION AND BLINDING

The Effectiveness and Implementation trials use cluster (site-level) randomization. Sites will be stratified by fidelity and healthcare organization prior to randomization. Those administering the surveys to patients will be masked to randomization status (and site). If survey administrators are inadvertently unmasked, that will be recorded and the rate of unmasking will be monitored. The analysis will examine the potential for bias as a result of making.

Study Multiple PIs will not have access to survey data until the last patient has completed the 6-month follow-up survey. The study statisticians and data analysts will have access to survey data, adverse events and randomization status to generate reports for DSMB meetings.

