8 STUDY ASSESSMENTS AND PROCEDURES

8.1 ENDPOINT AND OTHER NON-SAFETY ASSESSMENTS

Screening and Eligibility Assessment – To be enrolled/consented in the Effectiveness trial, a patient must have screened positive for OUD and a MHS in the past six months AND currently meet clinical criteria for ≥2 symptoms of OUD on the DSM-5 checklist *AND/OR OUD diagnosis recorded in the electronic medical record AND a patient encounter in the last 6 months OR OUD diagnosis on problem list PCP reviewed in the last 6 months.*

Survey Administration – Surveys will be administered at baseline, and at 3- and 6-month follow-ups.

Construct/Instrument	Baseline	3-Month Follow-Up	6-Month Follow-Up
Demographics	X		
Social Determinants	X		
Homelessness Screening Clinical Reminder	X		
Legal involvement question (Addiction Severity Index – modified)	X		
Insurance	X		
Pain (PEG)	X	X	X
Alcohol Use (AUDIT)	X	X	X
Opiate Use (BAM-R)	X	X	X
Opiate Craving Question (Addiction Severity Index – modified)	X	X	X
Readiness to Change (ICR)	X		
Other Drug Use (BAM- R)	X	X	X
Recent Experience of Overdose	X	X	X
Health Related Quality of Life (Veterans Short Form-12)	X	X	X
Depression (SCL20)	X	X	X
Anxiety (Neuro-QOL Measure - Anxiety, Short Form)	X	X	X
Trauma (PC-PTSD-5 Criteria A screener)	X	X	X
PTSD (PCL-5)	X	X	X
Access to Care (SPIRIT Perceived Access Inventory)	X	X	X
Service Utilization	X	X	X
Medication Use	X	X	X
Side Effects	X	X	X

Care Management Tracking System (CMTS) – After the last study participant has completed the 6-month follow-up, we will extract information from CMTS. CMTS is a web-based registry hosted by the AIMS Center and used by the care managers to track process and outcomes.²⁰ The CMTS contains clinic-level process of care and patient-level clinical outcome data that shows how patients receive care. For the evaluation, CMTS will be used to measure the number of care manager encounters, the number of

care manager encounters with recorded elements of BA, number of psychiatric case reviews, urine test results, medications prescribed for OUD and MHS, as well as results of state prescription drug monitoring checks to obtain an objective measure of MOUD initiation and adherence. For injectable buprenorphine or naltrexone, clinic staff will likewise record the administration of these injections in the CMTS.

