8.2.2 DEFINITION OF SERIOUS ADVERSE EVENTS

Definition of a Serious Adverse Events: Any adverse event temporally associated with the subject's participation in research that is potentially life threatening, results in death, requires hospitalization, results in persistent or significant disability/incapacity, or any other adverse event that, based upon appropriate medical judgment, may jeopardize the medical or surgical intervention to prevent one of the other outcomes listed here.

We will report the following Serious Adverse Events:

01. Suicide attempt
02. Suicide resulting in death
03. Death (not suicide or unsure if suicide)
04. Non-suicidal self-injury that resulted in Hospitalization
05. Non-suicidal self-injury that resulted in ED Visit
06. Non-lethal overdose (that resulted in hospitalization or ED visit)
07. Non-lethal overdose (that did not result in hospitalization or ED visit)
08. Non-lethal Overdose (with no hospitalization or ED visit)
09. Serious Medication Reaction (that resulted in a clinical encounter)
10. Other: _____

Serious Adverse Events will be classified as expected or unexpected; and as definitely study-related, probably study-related, possibly study-related, or definitely not study-related.

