10.1.6 STUDY MONITORING

Research staff at the University of Washington will meet with sites biweekly to review recruitment procedures including eligibility assessment and consenting, as well as facilitate adverse event reporting. Adverse Events reported from the sites will be promptly reviewed by a multiple PI to determine study relatedness. Adverse Events will be logged by sites into RedCap, which will automatically alert the multiple PIs via email until they are resolved. The multiple PIs and research coordinators will review eligibility and adverse event reports during weekly meetings.

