10.1.8 DATA HANDLING AND RECORD KEEPING

10.1.8.1 DATA COLLECTION AND MANAGEMENT RESPONSIBILITIES

Sources of Materials

Sources of research materials include the following:

EHR Data (Non-Indefinable) – Pre- and Post-Screening data (numerator [OUD diagnosis] and denominator [unique patients] will be calculated by each healthcare organization using EHR queries and recorded in an excel spreadsheet. The excel spreadsheet (which contains no patient health or identifying information), will be emailed to the study team at the University of Washington. Data will be reviewed by University of Washington statisticians and data managers and discussed with the on-site study team. This data will be used for the Secondary Objective (Pre-Post Trial).

Eligibility Data and Consent Forms – The eligibility information for all patients screening positive for OUD will be entered directly into RedCap by the on-site study team. Signed consents forms, will be scanned and attached to the RedCap study portal. Eligibility data will be reviewed by a University of Washington PI and the study coordinators, and discussed with the on-site study teams. This data will be used for the Primary Objective (Effectiveness trial).

Personal Identifying Information – Identifying information (e.g., name, address, telephone number, email, and contacts) about patients consenting to be in the Effectiveness trial will be stored in a single file along with a unique study identifier. This data will be used for the Primary Objective (Effectiveness trial).

Surveys - The patient web/telephone survey will be administered at baseline, 3- and 6-month follow-ups. All survey responses are stored directly into a RedCap database. This data will be used for the Primary Objective (Effectiveness trial).

Adverse Events – Information about all Adverse Events, Serious Adverse Events, Unanticipated Problems, and Potential Loss of Confidentiality will be entered directly into RedCap by the on-site study team and reviewed/edited by the research team. This data will be used for the Primary Objective (Effectiveness trial), as well as for regulatory purposes.

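### Overdoses disclosed on the 3- or 6-month survey are SAEs under Protocol 8.2.2 but have no stated route into the AE/SAE log or to investigator review

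*Protocol*

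**What the plan says.** - **Definition.** Protocol 8.2.2 lists non-lethal overdose as an SAE with hospital or emergency contact and, separately, without it: "Non-lethal overdose (that did not result in hospitalization or ED visit". For medication reactions the listed SAE is narrower: "Serious Medication Reaction (that resulted in a clinical encounter".
- **Where participants are asked.** The survey table in Protocol 8.1 includes "Recent Experience of Overdose" at baseline, 3 months and 6 months. It also has a side-effects item at the same times.
- **Who makes the entry.** Under Protocol 10.1.8.1, adverse event information "will be entered directly into RedCap by the on-site study team and reviewed/edited by the research team". Protocol 10.1.6 agrees: "Adverse Events will be logged by sites into RedCap, which will automatically alert the multiple PIs via email until they are resolved".
- **Who classifies.** Protocol 10.1.6: "Adverse Events reported from the sites will be promptly reviewed by a multiple PI to determine study relatedness".
- **Who may see survey answers during the trial.** Protocol 6.3: "Study Multiple PIs will not have access to survey data until the last patient has completed the 6-month follow-up survey". The next sentence gives access to others: "The study statisticians and data analysts will have access to survey data, adverse events and randomization status to generate reports for DSMB meetings". The same section masks survey administrators to arm and site.
- **Source of overdose data.** Protocol 9.4.3 takes overdose and the other mortality risk factors from the clinics through adverse event reporting. SAP section 3 takes them from both the survey and adverse event reporting.

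**The concern.** The protocol asks all participants, in both arms and on the same schedule, about an event that it defines as serious. It then assigns logging to people who do not receive the answer, and classification to people who are barred from it. An overdose with no hospital contact may be known only to the patient. Engagement with the care team is not required (Protocol 6.1.1 and 6.4), and the survey can be completed on the web (7.3), so the survey may be the only place where the event is disclosed.

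Two things are at stake. First, the SAE log and any count drawn from it would be incomplete for an event that the DSMB itself asked to have listed, according to the amendment history for version 7. Second, incompleteness may not be equal across arms. Protocol 6.1.1 has intervention care managers monitor opioid outcomes specifically, while the control arm refers opioid use disorder to specialty settings. Site-only counts could therefore show more overdoses in the intervention arm because more are heard about there. The primary outcomes are not affected.

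**Working it through.** The plan states no figure on this point, so the check traces one event through the text. Take a participant who overdoses after enrolment, has no hospital or emergency contact, and reports it only on the 3-month survey.

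1. **Is it an SAE?** Yes, by the list in Protocol 8.2.2.
2. **Who receives the answer?** It is stored in the REDCap survey database (10.1.8.1). During the trial 6.3 opens it to statisticians and analysts for DSMB reports and closes it to the multiple PIs.
3. **Who can open a log entry?** The on-site team (10.1.6, 10.1.8.1). The research team reviews and edits entries, which presupposes that an entry exists.
4. **Does anything pass the answer from step 2 to step 3?** Five places come close:
   - The schedule of activities (1.3) marks adverse event reporting at both follow-up surveys, but names no source and no hand-off.
   - Section 10.1.3 gives an escalation route for a participant who reports an intention to harm self or others. A past overdose is not covered.
   - Biweekly meetings with sites (10.1.6) help sites report adverse events. Nothing says that survey answers are brought to them.
   - Survey and adverse event data are eventually merged by study ID to build the analysis dataset (10.1.8.1). No comparison of the two is described.
   - Analysts may use survey data for DSMB reports (6.3). No section requires survey-reported overdoses to be shown, and 10.1.5 lists adverse events among the items for DSMB review without mentioning survey items.
5. **Which reporting clock applies?** Section 8.2.3.3 lists accidental overdose as an anticipated, non-study-related SAE. Under 8.2.5 expected SAEs go to the DSMB three times a year, related or not. The 10-business-day report applies to SAEs that are both unexpected and related.
6. **How long could PI review wait?** On the planned calendar, 33 months of enrolment + 6 months of follow-up = 39 months, which agrees with the synopsis. For an answer given at the first participant's 3-month survey, the wait is 39 − 3 = 36 months. For the last participant's 6-month survey it is 39 − 39 = 0. The wait therefore runs from 0 to 36 months, against a DSMB interval of 12 / 3 = 4 months. Consenting was later stopped (SAP section 6), so the actual calendar differs.
7. **Which survey reports count?** The baseline shell table (SAP Table S1) uses a 6-month lookback for overdose, and the follow-up recall period is not stated. If the same lookback is used at 3 months, it reaches 6 − 3 = 3 months before baseline, so some reports would predate enrolment. Baseline reports may also predate it.

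**The case against.** The strongest reply is that the gap matters less than it appears, because the body entitled to these events can be reached another way. Expected overdoses go to the DSMB at intervals, and the staff who write the DSMB reports can see survey data. Coordinators are not barred from survey data, university staff meet sites biweekly, and outreach to patients not engaged in care belongs to both arms (Table 1 in 6.1.1). Much of this stands, and it rules out several stronger readings that a reader might infer:

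- *That 10-business-day reports are being missed.* For accidental overdose the ordinary route is the periodic DSMB report. The shorter clock would apply only to an overdose judged unexpected and related. An event that is never logged cannot receive that judgement.
- *That the DSMB is blind to these events.* The documents do not show this. They allow survey data in its reports but do not require it.
- *That side effects reported on the survey are lost SAEs.* Section 8.2.2 lists only serious medication reactions that led to a clinical encounter, and 8.2.3.3 anticipates side effects.
- *That a disengaged patient's overdose necessarily goes unlogged.* The clinic may learn of it by outreach or at a later visit. The text supports only the absence of a route from the survey.
- *That a count can be given.* With 254 enrolled (SAP section 6), an assumed 5% to 10% disclosing an overdose and an assumed half unknown to the clinic, 254 × 0.05 × 0.5 = 6.4 and 254 × 0.10 × 0.5 = 12.7. With the 20% attrition in Protocol 9.2, 254 × 0.8 × 0.05 × 0.5 = 5.1 and 254 × 0.8 × 0.10 × 0.5 = 10.2. Neither assumed rate is in the documents, so these products are not evidence of size. The 36 months is likewise a single worst case.

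None of this supplies the hand-off. An aggregate line in a DSMB report creates neither a log entry nor a relatedness judgement.

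**Conclusion.** The concern holds for non-lethal overdoses after enrolment that are disclosed on the 3- or 6-month survey and, secondarily, for medication reactions that meet the 8.2.2 definition. Followed as written, site entry together with the bar on PI access leaves such events without a stated route into the AE/SAE log or to relatedness review. Protocol 9.4.3 and SAP section 3 also disagree on the source of overdose data and give no rule for combining the two.

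The size cannot be computed: the documents give neither the disclosure rate nor the share already known to clinics. Unequal capture by arm is a reasonable inference from the difference in care-manager monitoring, not a demonstrated bias. The conclusion is limited to the available text, which lacks some of the governance text around Protocol 10.1.4.

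**What to change.** Amend Protocol 6.3, 10.1.6 and 9.4.3 as follows:

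- Before each DSMB report, and again before final analysis, a coordinator who is not a PI, or the analyst who already has survey access, matches survey-reported post-enrolment overdoses and medication reactions meeting 8.2.2 to the AE/SAE log.
- Each unmatched event gets an entry carrying only the event and study ID, for PI classification under the existing 8.2.5 timetable. Outcome scores stay closed to the PIs.
- Survey-only and site-reported events are tabulated by arm for the DSMB and in the final report.
- The recall period of the overdose item at each survey is stated, with a rule for excluding pre-enrolment events and for not counting one event at two surveys.
- Protocol 9.4.3 and SAP section 3 are reconciled on the source of overdose data.

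Consenting has stopped, so any DSMB reports already made cannot be changed. The pass before final analysis is still worth making.

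The practical cost is modest. Surveys and the log are both in REDCap and share a study ID. The work is mainly matching duplicates, and PIs gain limited sight of individual survey-reported events. The larger cost arises if an event is passed to the site for verification. Protocol 2.3.3 undertakes to keep survey answers strictly confidential and available only to the study team, so protocol and consent wording would have to change. Participants who expect disclosure to their clinic may also answer less candidly, on a survey that carries the self-reported opioid outcome. That trade-off should be decided openly before any site verification is added.
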